4.3.2 Efficacy measurements

Patients with non-measurable disease only are not excluded from this study.

4.3.2.1 Tumour assessment for patients with measurable disease

Tumour assessment will be performed using RECIST criteria for patients with measurable disease. The RECIST guidelines for measurable, non-measurable, target and non-target lesions, and the objective tumour response criteria (complete response [CR], partial response [PR], stable disease [SD] or PD) are presented in [Appendix C](#). The RECIST criteria will be used to programmatically determine Objective Response Rate (ORR) and Best Overall Response.

Baseline radiological tumour assessments should be performed no more than 4 weeks before the start of study treatment, but should be as close as possible to the start of study treatment. After the start of repeat dosing (day R1), efficacy for all patients with measurable disease will be assessed by objective tumour response every 6 weeks (relative to day R1). Assessments may be performed ± 7 days relative to the specified visit date.

Baseline CT examination will be performed on anatomical coverage to adequately define all areas of disease. Post-baseline imaging should follow and evaluate all previous identified lesions. MRI should only be used where CT is not feasible or if it is medically contra-indicated.

All measurable lesions confirmed and assessed by radiological methods (CT or MRI scans) up to a maximum of 5 lesions per organ and 10 lesions in total, representative of all involved organs, should be identified as target lesions, recorded and measured at baseline, and at the time points specified above.

Lesions that have been previously irradiated should not be considered measurable lesions.

Non-target lesions will also be monitored throughout the study, and an assessment of non-target lesions will be made and recorded as “present”, “present with progression” or “absent”.

Details of any new lesions will also be collected.

It is important to follow the assessment schedule as closely as possible. If an unscheduled radiological and clinical tumour assessment is performed, and the patient has not progressed, the next scheduled tumour assessment should still be performed at the planned time (as detailed in the study plan, [Table 1](#)).

Tumour assessment will be performed in accordance with the protocol schedule until evidence of one of the following:

- Objective PD
- Death
- Withdrawal of informed consent
- Withdrawal from study therapy.

A patient will be determined to have progressed if they have progression of target lesions, clear progression of existing non-target lesions, or the appearance of one or more new lesions.

Unequivocal malignant disease not identified prior to starting study treatment on additional anatomical imaging (eg, CT, MRI or plain X-ray), prompted by symptoms is considered disease progression and should be recorded as new lesions. If progression is uncertain, patients should continue on treatment until the next scheduled assessment (ie, 6 weeks later ± 7 days) or may have an unscheduled assessment earlier than this if considered appropriate by the investigator.

Lesions must be assessed using the same method and technique on each occasion. Lesions will be recorded on the CRF page in the same order as they were recorded at screening.

Details of any new lesions will also be collected. Response will be calculated in comparison to the baseline tumour measurements obtained before starting treatment. Progression will be calculated in comparison to when the tumour burden was at a minimum. Overall visit response will be recorded on the CRF.

Categorisation of overall visit response will be based on RECIST using the following response categories: CR, PR, SD, and PD (see [Appendix C](#)). To be assigned a best overall response of PR or CR, changes in tumour assessments must be confirmed no less than 4 weeks after the criteria for response were met. For a best overall response of SD, measurements must have met the SD criteria at least once after start of study treatment for a minimum interval of 6 weeks.

Measurable lesions will also be used to monitor the change in tumour length, which will also be used as a preliminary assessment of efficacy.

4.3.2.2 Tumour assessment by imaging techniques for patients with non-measurable disease only at baseline

For patients with non-measurable disease only at baseline, other measures of efficacy for patients can be used at investigator discretion. In these cases, the investigator will decide the imaging methods used and the schedule of the tumour assessments.

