Patients will be evaluable for the dose escalation set if they have experienced a DLT, or received at least 80% of planned doses of AZD8931 and who had all safety assessments completed during the DLT evaluation period.

A minimum of 3 and a maximum of 6 eligible patients will be dosed initially. At the discretion of the SMC, or if a patient within a dose cohort experiences a DLT additional patients will be enrolled to ensure that the cohort includes a maximum of 6 evaluable patients. The dose may be escalated in the next cohort if the SMC declares the dose level in the current

cohort as tolerable. The dose level in the current cohort is defined as intolerable according to the algorithm in Section [3.1.2](#).

The dose of AZD8931 will initially be escalated by dose doubling, up to a level where the SMC decides that smaller escalation steps are warranted. Based on emerging data including PK and/or safety data and/or pre-clinical data, the SMC can consider alternative schedules including once-daily dosing and intermediate dose levels. There will be adequate time between dose groups to allow review of relevant safety and PK data by the SMC.

Target patient population

Adult patients with advanced solid malignancies will be eligible for enrolment into this study.

Investigational product, dosage and mode of administration

AZD8931 is available as four strengths of plain, round, biconvex, white film coated tablets containing 2.5 mg, 10 mg, 40 mg and 100 mg of AZD8931 (expressed as free base). Tablets to be taken orally.

The starting dose will be 40 mg, based on the results of the single ascending dose (SAD) study, D0102C00001.

Dosing will be once only on Day 1, followed by a 4-day observation period. Multiple dosing can start between Day 5 and Day 7, and will be twice daily for 21 days (days R1 to R21). For example, if the dose level is 40 mg, the patient will receive 40 mg on Day 1 (D1), then 40 mg twice daily (total 80 mg per day) on Days R1 to R21.

AZD8931 should continue to be administered beyond the DLT evaluation period if, in the investigators opinion, the patient is experiencing or may receive some benefit from therapy, is free from intolerable toxicity and has not met a discontinuation criterion.

Safety Monitoring Committee

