1.2.4 Rationale for efficacy assessments

As an exploratory objective, the anti-tumour activity of AZD8931 will be investigated. Patients who complete the DLT evaluation period and who do not meet any discontinuation criteria are permitted to continue on the study. Efficacy will be assessed by means of Response Evaluation Criteria In Solid Tumours (RECIST) evaluations, and by changes in

tumour length, every 6 weeks (relative to the first day of AZD8931 dosing). Results will be preliminary only, but will be used to aid design of future studies.

This study will be conducted in compliance with the protocol, International Conference on Harmonisation (ICH) Good Clinical Practice (GCP) and applicable regulatory requirements.

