Blood samples for proapoptotic biomarkers (optional)		x ^{l,n}					x ^l	x ^l	x ^l	x ^l	x	x ^l	x ^g
Blood sample for pharmacogenetics (optional)		x ^o											
Urine sample for urinalysis	x	x ^l	x	x	x	x	x	x	x	x	x	x	x
Patient diary (including times study drug taken on PK days, and survey of ophthalmological [weekly] and other symptoms)						x ^p	x ^p	x ^p	x ^p	x ^p		x ^p	

Table 1 Study plan

Assessments	Screening	DLT Evaluation Period ^a									Premature discontinuation	Continuation beyond R21 ^a	Post-study follow-up
		Single dose											
Day (h = hours)	D-21 to D0	D1	D2 (24 h)	D3 (48 h)	D4 (72 h)	D5 to D7						Every 3 weeks	7 days after last dose
Repeat dosing (R) day (d=day)						R1	R3	R7 ±1d	R14 ±1d	R21 ±1d	≤2d	±3d	±1d
Concomitant medications	x	x	x	x	x	x	x	x	x	x	x	x	x
Adverse events	x	x	x	x	x	x	x	x	x	x	x	x	x

TNM = Tumour, Node, Metastases; RECIST = Response Evaluation Criteria In Solid Tumours; HbA1c = glycosylated haemoglobin

Notes to study plan

^a Treatment should be extended beyond day R21 if, in the investigator's opinion, the patient is receiving or may receive some benefit from therapy is free from intolerable toxicity and has not met a discontinuation criterion (see Section 3.3.5.1).

^b Baseline radiological tumour assessments should be performed no more than 4 weeks before the start of study treatment, but should be as close as possible to the start of study treatment.

^c Where possible and appropriate.

^d Every 6 weeks (±7 days), relative to day R1, until objective disease progression, study drug discontinuation, withdrawal of informed consent or death (whichever is soonest).

^e No food is allowed from 2 hours before to 2 hours after study drug dosing.

^f Full examination at screening (see Section 4.4.4). Full examination at other visits only if clinically significant abnormalities are observed. Brief symptom-directed examinations, or follow-up of existing abnormalities, should be performed at study visits, as appropriate.

^g Only if not performed at day R21 (or premature discontinuation visit).

^h Full ophthalmological assessment will be done at screening. Thereafter it will be done at premature discontinuation or day R21, whichever is earliest. Beyond day R21, questionnaire survey will be done every cycle or at discontinuation, with full examination only if indicated in accordance with the protocol.

ⁱ Every 9 weeks for 3 times, then every 18 weeks.

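### The 6-week minimum for stable disease has no tolerance, so a first scan early in the permitted ±7-day window can fall just short of it

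*Protocol*

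**What the plan says.** Four statements in the Protocol bear on this.

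- **SD rule, Section 4.3.2.1.** The SD criteria must have been met "at least once after start of study treatment for a minimum interval of 6 weeks". No visit window is attached.
- **Scan schedule, Section 4.3.2.1.** Patients with measurable disease "will be assessed by objective tumour response every 6 weeks (relative to day R1"), and "Assessments may be performed ± 7 days relative to the specified visit date". Table 1 note d agrees: "Every 6 weeks (±7 days), relative to day R1".
- **Scan schedule, Section 1.2.4.** Here efficacy is assessed "every 6 weeks (relative to the first day of AZD8931 dosing"), which is D1 rather than R1.
- **Lag between the two days, synopsis.** "Multiple dosing can start between Day 5 and Day 7", so R1 falls 4 to 6 days after D1.

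Section 6.1.4 takes best overall response from the start of study drug and has it derived by program. Appendix C, Section 4.3.3, also defines best overall response, but gives neither an SD minimum nor a window rule.

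**The concern.** The scan window opens before the minimum interval that the same section imposes. A patient can be scanned on protocol, show SD, progress at the next scan, and still miss the SD definition. Another patient with the same disease course, scanned a few days later, would meet it. A program applying the 42-day limit literally would separate the two on appointment date alone. The error runs one way: an early scan can lose SD, and no scan gains it.

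The two scan anchors add to the problem, because the size of the gap depends on which is used and on whether treatment is taken to start on D1 or R1. Appendix C does not settle it. Read alone, it would credit SD to the patient whom Section 4.3.2.1 excludes.

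**Working it through.** The Protocol gives no figure of its own to reproduce, so this is a day count.

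**Inputs**
- SD minimum: 6 weeks = 42 elapsed days from start of treatment (Section 4.3.2.1).
- First scan due: anchor + 42 days, window −7 to +7, giving 15 permitted days (Section 4.3.2.1; Table 1 note d).
- Lag L from D1 to R1: 4, 5 or 6 days for R1 on Day 5, 6 or 7 (synopsis).

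**Formula.** With scans anchored to R1, the window in days after D1 runs from L + 35 to L + 49. A scan day fails if fewer than 42 days have passed since start of treatment.

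**Start of treatment = D1, scans from R1**
- L = 4: window 39 to 53; days 39, 40 and 41 fail, 3 of 15.
- L = 5: window 40 to 54; days 40 and 41 fail, 2 of 15.
- L = 6: window 41 to 55; day 41 fails, 1 of 15.

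**All four combinations**

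| Start of treatment | Scan anchor | Days failing, of 15 | Largest shortfall |
|---|---|---|---|
| D1 | R1 | 3, 2 or 1 | 3, 2 or 1 days |
| D1 | D1 | 7 (days 35 to 41) | 7 days |
| R1 | R1 | 7 (days 35 to 41) | 7 days |
| R1 | D1 | 11, 12 or 13 | 11, 12 or 13 days |

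No combination brings the count to zero.

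**When SD is actually lost.** The second scheduled scan is at R1 + 84 ± 7, which is L + 77 to L + 91, or day 81 to 97 after D1 across L = 4 to 6. SD at that scan, or at any other scan on or after day 42, restores the category. Loss therefore needs an early first scan, SD at that scan, and no later SD assessment.

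**Check of the remedy.** With scans from R1 and a minimum of 35 days after R1, the earliest permitted scan is R1 + 35, so 0 of 15 days fail. If scans stayed anchored to D1, the earliest would be 35 − L = 31, 30 or 29 days after R1, and the 35-day minimum would still be missed by 4 to 6 days. One anchor and the shorter minimum are both needed.

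**The case against.** The strongest reply is that the mismatch is small and nothing is decided on it. Section 4.3.2.1 and Table 1, which set the scan schedule for sites, both use R1; Section 1.2.4 is only a rationale paragraph. Start of treatment most naturally means the first dose: Section 3.1.2 opens the DLT period at first administration, and Section 4.3.2.1 separately calls R1 the start of repeat dosing. On that reading the lag absorbs most of the early window and the gap is 1 to 3 days. This stands, and it sets the size of the point.

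It is also true that window days are not patients. Section 4.3.2.1 asks sites to keep closely to the schedule, so an even spread of scans over the 15 days cannot be assumed. A later unscheduled scan, or one at premature discontinuation, can also rescue SD, although Table 1 note c asks for the latter only where possible and appropriate.

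Two replies carry less weight. One is that a full 6 weeks is a legitimate, conservative definition. It is, but then the scan window should not open before it. The other is that the SAP can supply a tolerance. A SAP commonly does, but here the Protocol itself fixes both the minimum and the window, so a tolerance in the SAP would depart from the Protocol's own rule.

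**Conclusion.** The inconsistency is real under every reading, and its effect is small. Taking D1 as start of treatment and R1 as scan anchor, the first 1 to 3 of 15 permitted days cannot yield SD; with a common anchor it is 7 of 15. The Protocol allows no estimate of how many patients are affected, because it gives neither a distribution of scan dates nor a progression rate.

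The consequence is a slight downward misclassification of SD, dependent on scheduling, in an exploratory and descriptive endpoint. Objective response rate counts only complete and partial responses and is unaffected; so are the tumour-length plots, DLT and MTD.

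A reader might infer more than this:
- *That scans are routinely a full week short.* This needs both clocks on the same day, which is not the natural reading.
- *That a main activity signal is biased.* The Protocol defines no SD rate or disease-control endpoint. The efficacy objective names RECIST and change in tumour length, and Section 1.2.4 calls the results preliminary.
- *That many patients will have only one scan before progression.* That is plausible in refractory disease, but the document gives no figure for it.

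**What to change.** - In Section 1.2.4, count scans from R1, as Section 4.3.2.1 and Table 1 note d already do.
- In Section 4.3.2.1, state the SD minimum as 6 weeks less the 7-day visit window: at least 35 days after R1. Every first scan within the window then qualifies.
- Leave Section 6.1.4 as it is. It sets no scan schedule, and its reference to the start of study drug does no harm.

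The cost is wording in two sections and one constant in the response derivation, with no extra scans. The downside is a slightly shorter SD requirement. Measured from D1, 35 days after R1 is day 39, 40 or 41, so the minimum falls by 3, 2 or 1 days. If the present 6 weeks is read as running from R1, it falls by 7 days. The change can only raise the SD count, so it should be made before the derivation is programmed.

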4.4 Safety measurements

4.4.1 Laboratory safety measurements

Blood and urine samples for determination of clinical chemistry, haematology and urinalysis parameters will be taken at the times given in the study plan (see [Table 1](#)). Additional safety samples may be collected if clinically indicated at the discretion of the investigator. The date and time of blood and urine sample collection will be recorded on the appropriate CRF.

Blood samples should be collected for all clinical chemistry and haematology parameters. Fasting samples are not required for this study (except if random blood glucose is >13.9 mmol/L then a fasting blood glucose [minimum 8 hours fast without sugar-containing drinks] is recommended to confirm hyperglycemia).

The laboratory assessments will be performed locally at each centre's laboratory by means of their established methods.

Glucose and potassium monitoring: On Days D1 and R14 a blood sample should be taken at 6 hours post-dose for measurement of potassium and glucose levels only. Additional monitoring of potassium should be undertaken if the patient receives drugs that may cause hyperkalemia. Hyperkalemia should be managed according to local standards. Hyperglycemia should be managed according to local standards.

Females of child bearing potential must give a sample of the first urine passed during the day (see [Table 1](#)) for a pregnancy test to be performed.

All laboratory safety analyses will be performed by a local laboratory.

The following laboratory variables will be measured:

Clinical chemistry

P – Urea
P – Creatinine
P – Glucose (fasting^b)
P – Sodium
P – Potassium
P – Calcium
P – Albumin
P – Total bilirubin
P – Alkaline phosphatase
P – AST
P – ALT
P – Gamma glutamyltransferase
P – Lactate dehydrogenase
P – Unconjugated bilirubin (if total bilirubin elevated)

Additional analyses at screening only

P – Activated partial thromboplastin time
P – International normalisation ratio
B – HbA1c

Haematology

B – Haemoglobin
B – Erythrocyte count
B – Haematocrit
B – Platelet count
B – Total leukocyte count
B – Mean cell haemoglobin concentration
B – Mean cell volume
B – Mean cell haemoglobin
B – Monocytes (absolute)
B – Eosinophils (absolute)
B – Basophils (absolute)
B – Neutrophils (absolute)
B – Lymphocytes (absolute)

Urinalysis

U – Glucose
U – Protein^a
U – Blood^a
U – Urine sediment microscopy (Crystals, Casts, Epithelial Cells, Leucocytes and Erythrocytes)

^a If blood or protein are present at $\geq +$, urine sediment microscopy will be performed on the sample.

^b Fasting glucose only if random blood glucose is >13.9 mmol/L.

B – Blood, P – Plasma, U – Urine

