Dose-related increases in plasma glucose have been observed following administration of oral doses to dogs. Increases were reversed by 24 hours post-dose and were generally associated

with increases in plasma cortisol. The insulin response to the glucose elevation appeared to be attenuated/absent especially at high plasma levels of AZD8931.

AZD8931 was shown to be positive in an in vitro 3T3 Neutral Red Uptake phototoxicity test. Radioactivity was detected in both the skin and uveal tract in a rat quantitative whole-body autoradiography study with AZD8931. These data indicate a potential phototoxicity risk of AZD8931.

Reproductive and developmental toxicity studies, and local tolerance studies, have not been conducted.

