3.1.6 Study flow chart and study plan

Figure 2 Study flow chart

3 to 6 patients	Single dose	4-day observation period	Twice daily dosing for 21 days	Data collection /review	SMC review	Single dose	4-day observation period	Twice daily dosing for 21 days...
Day	D1		D5 to 7			(1)		
Repeat dosing day			R1.....R21					

(1) New dose group (increased dose, same dose, decreased dose) depending on result of SMC meeting to discuss previous dose cohort of 3 to 6 evaluable patients (see Section 6.6).

Abbreviations: SMC: Safety Monitoring Committee. Shading: AZD8931 treatment.

Table 1 Study plan

Assessments	Screening	DLT Evaluation Period ^a									Premature discontinuation	Continuation beyond R21 ^a	Post-study follow-up
		Single dose											
Day (h = hours)	D-21 to D0	D1	D2 (24 h)	D3 (48 h)	D4 (72 h)	D5 to D7						Every 3 weeks	7 days after last dose
Repeat dosing (R) day (d=day)						R1	R3	R7 ±1d	R14 ±1d	R21 ±1d	≤2d	±3d	±1d
Informed consent (main study, genetics [optional], proapoptotic biomarkers [optional])	x												
Inclusion/exclusion criteria	x												
Tumour TNM stage at diagnosis and at study entry (and ErbB2 status, if available)	x												
Tumour assessment (RECIST)	x ^b										x ^c	x ^d	
Chest X-ray	x												
Demographics	x												
Medical/surgical history	x												
Previous anticancer therapy, including surgery	x												
Urine pregnancy test	x												
Administer AZD8931		Single dose ^e				Twice daily for 21 days ^e						Twice daily ^e	
Physical examination	x										x		x
Dermatological examinations ^f	x									x	x		x ^g

Table 1 Study plan

Assessments	Screening	DLT Evaluation Period ^a									Premature discontinuation	Continuation beyond R21 ^a	Post-study follow-up
		Single dose											
Day (h = hours)	D-21 to D0	D1	D2 (24 h)	D3 (48 h)	D4 (72 h)	D5 to D7						Every 3 weeks	7 days after last dose
Repeat dosing (R) day (d=day)						R1	R3	R7 ±1d	R14 ±1d	R21 ±1d	≤2d	±3d	±1d
Ophthalmological assessments	x									x	x	x ^h	x ^g
Echocardiography	x									x	x	x ⁱ	x ^g
12-lead Electrocardiogram ^j	x	x ^k	x	x	x	x	x ^l	x ^l	x ^k	x	x	x	x
Vital signs (heart rate, blood pressure)	x	x ^k	x	x	x	x	x ^l	x ^l	x ^k	x	x	x	x
Blood sample for AZD8931 pharmacokinetic (PK) analysis		x ^k	x	x	x		x ^l	x ^l	x ^k				
Blood sample for clinical chemistry, haematology, coagulation parameters	x	x ^{l,m}	x	x	x	x ^l	x ^l	x ^l	x ^{l,m}	x ^l	x	x	x

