Patients with random blood glucose above 11.1 mmol/L at screening will be excluded from the study. Those with impaired glucose tolerance would be included only if their fasting blood glucose levels are recorded within non-diabetic ranges. Blood glucose levels will be monitored during the study. In the event of a patient developing significant hyperglycemia (fasting glucose >13.9 mmol/L), that cannot be attributed to any other cause, this will be deemed as a DLT. The evaluation of post-prandial glucose as an assessment of a patient's glycemic state in this study population may be confounded by disease burden, concomitant medications (steroids), study conditions (food restrictions, disturbed circadian activity, mobility etc). The clinical picture of day-to-day glycemic state obtained from random pre- and post-dose glucose samples may not reflect the true glycemic state.

Patients with history or evidence of cardiac dysfunction will be excluded from the study and a baseline echocardiogram and digital ECG will be used to reference any symptomatic or non-symptomatic deterioration in cardiac function that may happen during the study.

Patients with history or evidence of interstitial lung disease will be excluded from the study and baseline radiology will be used to compare the findings associated with any respiratory symptoms later in the study.

Patients in this study will be advised of the need for sun protection measures such as avoidance of sun beds, the application of sun-cream (sun protection factor [SPF] minimum 15) to body parts exposed to the sun, and the use of sunglasses in sunny conditions. Patients will be advised to adopt such measures for a period of 3 months after receiving their final dose of AZD8931.

No reproductive toxicology studies have been conducted to assess safety to the human foetus. AZD8931 has not shown any genotoxic potential. It is not known whether AZD8931 or its metabolites are secreted in human milk or semen. Therefore, until further data is available, AZD8931 is not suitable for administration to pregnant or nursing women, and conception

while on treatment must be avoided. For AZD8931 studies, male subjects will be required to abstain from unprotected sex and sperm donation for 4 months following dosing, and will be advised to use condoms in addition to a second reliable form of contraception for a specified period.

Finally, all safety data will be collected on a regular basis and reviewed by the principal investigator.

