3.3.2 Inclusion criteria

For inclusion in the study, patients must fulfil all of the following criteria:

1. Provision of written informed consent
2. Male or female aged ≥ 18 years
3. Cancer which is refractory to standard therapies, or for which no standard therapies exist. Inclusion is irrespective of stage of disease or extent of prior therapy
4. Histologically or cytologically confirmed solid, malignant tumour
5. World Health Organization (WHO) performance status 0 to 2 (those with performance status 2 must have been stable with no deterioration over the previous 2 weeks) (see [Appendix D](#))
6. Adequate haematology, liver function and biochemistry tests:
Absolute neutrophils count $>1.5 \times 10^9/L$, platelets $>100 \times 10^9/L$, haemoglobin ≥ 9 g/dL (5.59 mmol/L) (blood transfusion, iron and/or erythropoietin therapy are permitted at the discretion of the investigator, and must be recorded in the concomitant medications page of the case report form [CRF])
Serum bilirubin ≤ 1.5 x upper limit of normal (ULN), and alkaline phosphatase, aspartate aminotransferase (AST) and alanine aminotransferase (ALT) ≤ 2.5 x ULN, except in patients with liver or bone metastases [ALT, AST and alkaline

phosphatase ≤ 5 x ULN]
International normalisation ratio and activated partial thromboplastin time
<1.2 x ULN

7. Adequate cardiac function (baseline LVEF higher than the institution's lower limit of normal range, determined by echocardiography)
8. Negative screens for serum hepatitis B surface antigen, hepatitis C antibody and human immunodeficiency virus (HIV)
9. Likely ability to complete 3 weeks continuous treatment
10. Female patients with evidence of post-menopausal status or pre-menopausal patients must use acceptable (to AstraZeneca) contraception and follow the study restrictions (see Section 3.3.4). There must be a negative urinary pregnancy test for female pre-menopausal patients.
Post-menopausal females are defined as follows: Natural menopause with last menses at least 1 year ago; radiation induced oophorectomy with last menses >1 year ago; chemotherapy induced menopause with last menses >1 year ago; serum follicle stimulating hormone and luteinising hormone and plasma oestradiol levels in post-menopausal range for the institution; bilateral oophorectomy or hysterectomy

For inclusion in the **exploratory biomarker component** of the study (optional), patients must fulfil the following criterion:

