4.1 Medical examination and demographic measurements

4.1.1 Enrolment medical examination and demographic measurements

The following screening and demographic data will be collected in the paper CRF (pCRF) in the 21 days prior to the first treatment visit (see [Table 1](#) for the timing of these assessments).

- Provision of written informed consent
 - Provision of written informed consent must be obtained at screening for all patients. Additional written informed consent for participation in the genotyping component and biomarker analysis is optional
- Date of birth, sex, height, weight and race
- Relevant medical and surgical history, including menstrual status, concurrent illness and recent and current medications
- Urine pregnancy test
- Previous anti-cancer therapy, including surgery (concomitant medications will be recorded from Screening until the Study Completion Visit)
- Echocardiography and ECG
- Chest X-ray
- Physical examination, including but not limited to the following body systems: general appearance, skin, head and neck, lymph node, thyroid, musculoskeletal/extremities, cardiovascular, lungs, abdomen, and neurological
- Safety blood sampling and urine sampling
- Dermatological examination (observational and symptom-directed)
- Ophthalmological examination (see Section [4.4.5](#))

- Vital signs (resting BP and heart rate, measured with the patient in a sitting position)
- Type of tumour, TNM (tumour, node, metastases) stage at diagnosis and at study entry, and ErbB2 status (if available)
- Tumour assessment according to local standards to define all areas of disease (eg, bone, liver and lung). Document measurable disease according to RECIST criteria (see [Appendix C](#)), using Computer tomography (CT) or magnetic resonance imaging (MRI) scan. The baseline tumour assessment must be within 4 weeks prior to the start of treatment. This does not need to be repeated prior to starting treatment unless the investigator believes that there has been a change in tumour burden. If imaging is repeated before study entry, the most recent assessment should be recorded as the screening assessment. For patients with prior first line chemotherapy the screening imaging tests must have been performed at least 4 weeks after the last cycle of prior chemotherapy.

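### The pregnancy test is scheduled once, at Screening, so the negative result can be about 21 days old at first dose and 45 to 47 days old at R21, with no retest planned during open-ended dosing

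*Protocol*

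**What the plan says.** Section 4.4.1 states: "Females of child bearing potential must give a sample of the first urine passed during the day". It leaves the timing to Table 1.

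In Table 1 (section 3.1.6) the row "Urine pregnancy test" has one mark, under Screening, D-21 to D0. Section 4.1.1 agrees. It lists the test under this lead-in: "The following screening and demographic data will be collected in the paper CRF (pCRF) in the 21 days prior to the first treatment visit".

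Inclusion criterion 10 (3.3.2) reads: "There must be a negative urinary pregnancy test for female pre-menopausal patients". It gives no limit on how old that result may be at first dose.

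On the risk, 1.1.1.3 records: "Reproductive and developmental toxicity studies, and local tolerance studies, have not been conducted". Section 3.2.2 concludes that "AZD8931 is not suitable for administration to pregnant or nursing women" and that conception during treatment must be avoided.

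On duration, the synopsis says "AZD8931 should continue to be administered beyond the DLT evaluation period" for patients who may benefit, tolerate the drug and meet no discontinuation criterion. No end date is set.

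**The concern.** The protocol treats pregnancy as a reason to stop the drug. Section 3.3.5.1 names a positive pregnancy test among the safety reasons for discontinuation, and 8.4 requires study drug to stop at once if a patient becomes pregnant or tests positive during the study. After Screening, no scheduled assessment can produce that result.

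A woman who conceives after the Screening test would go on being dosed until she reports it or someone orders an unscheduled test. What is at stake is avoidable foetal exposure to a drug with no reproductive toxicity data. This is a weakness in safety monitoring. The sections do not contradict one another, and no statistical quantity depends on it. A visit schedule belongs in the protocol, so a SAP would not be expected to supply it.

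**Working it through.** The protocol gives no figure for the age of the test result, so there is none to reproduce. The check is calendar arithmetic.

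**Inputs**
- Earliest Screening test: 21 days before D1 (4.1.1).
- R1 falls on D5 to D7, and repeat dosing lasts 21 days (synopsis, 3.1.1), so R21 = R1 + 20 = D25 to D27.
- Day 1 of cycle 2 is the day after R21 (3.4.2.1), so D26 to D28.
- Continuation visits are every 3 weeks (Table 1).

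**Age of the last scheduled result, as written** (visit day minus test day)

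| Visit | Days after D1 | Test 21 days before D1 |
|---|---|---|
| D1 | 0 | 21 |
| R21 | 25 − 1 = 24 to 27 − 1 = 26 | 21 + 24 = 45 to 21 + 26 = 47 |
| Day 1 of cycle 2 | 25 to 27 | 21 + 25 = 46 to 21 + 27 = 48 |

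Table 1 labels the window D-21 to D0. If D0 is the day before D1, each age rises by 1 day: 22 at D1 and 46 to 48 at R21. At the other extreme, a test done on D0 is 1 day old at D1 and 25 to 27 days old at R21. After R21 the age grows without limit, because no later test is scheduled.

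**With the proposed schedule**
- At D1 the result is current (0 days).
- D1 to the end-of-cycle-1 test: 24 to 26 days if done at R21, or 25 to 27 days if done on day 1 of cycle 2.
- End of cycle 1 to the next 3-weekly visit, tested at R21: 21 days if visits are counted from R21, or 22 if counted from day 1 of cycle 2.
- The same interval, tested on day 1 of cycle 2: 20 or 21 days.
- Between later continuation visits: 21 days.

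Visit windows (R21 ±1 day, continuation ±3 days) are left out of all these figures.

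**Are the visits already there?** The Table 1 row "Urine sample for urinalysis" is marked at D1 pre-dose, R21, premature discontinuation, the continuation visits and follow-up. Urine is therefore already collected at every proposed visit. Day 1 of cycle 2 has no column of its own in Table 1, but 3.1.2 places pre-dose assessments on that day.

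**The case against.** The strongest reply is that the protocol deliberately relies on prevention, and does so strictly. Criterion 10 requires a negative test at entry. Criterion 31 excludes patients of reproductive potential who do not use reliable birth control. Section 3.3.4 asks for abstinence or two methods, one of them highly effective (IUD, tubal ligation or a vasectomised partner), from Screening until at least 28 days after the last dose. It also requires counselling on foetal risk. Section 4.4.1 allows extra safety samples when clinically indicated, and 8.4 fixes the response to a pregnancy. The ages above are worst cases and do not measure the probability of exposure. The 3-weekly interval is a choice, a test after the last dose cannot prevent exposure, and a false positive would trigger the stopping rule in 8.4.

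Much of this stands. Pregnancy should be uncommon, the figures are upper bounds, and the protocol sets no retest interval. But contraception, counselling and discretionary samples are prevention or ad hoc testing, and none is planned detection. Sections 3.3.5.1 and 8.4 also make the gap clearer, because they act on a result that the schedule never generates after Screening. A test at the end of treatment still helps, since 8.4 requires the outcome of every pregnancy to be followed up. False positives are a minor cost and can be handled by confirming a positive strip.

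**Conclusion.** The concern holds. Followed exactly, the protocol allows a first dose on a pregnancy result about 21 days old. It reaches R21 on a result 45 to 47 days old and continues dosing indefinitely with no planned retest. These figures assume the test is done at the start of the window, take the 21 days of 4.1.1 and ignore visit windows; the Day 0 numbering in Table 1 would add 1 day.

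The number of women affected cannot be derived from the protocol, and the contraception rules should keep it small. The MTD, the PK and the analyses are unaffected. The schedule should be changed because the harm is avoidable and the remedy is cheap.

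**What to change.** In the pregnancy-test row of Table 1, for women of child-bearing potential, add marks at:

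1. D1, pre-dose.
2. The end of cycle 1, once: either R21 or pre-dose on day 1 of cycle 2. These are consecutive days, so one test is enough.
3. Each 3-weekly continuation visit.
4. Premature discontinuation or the post-study follow-up about 7 days after the last dose, once. This also covers a woman who leaves before R21.

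The 3-weekly interval is proposed because it uses existing visits.

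The cost is one urine strip per marked visit, with no new visit and no extra blood. These women would also have to bring a first-of-day sample, as 4.4.1 asks, which Table 1 does not require for urinalysis. Because a positive test leads to immediate discontinuation under 8.4, the sponsor may wish to state how a positive strip is confirmed.
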